5.3 Informed Consent Procedures

A waiver of informed consent and HIPAA authorization will be used for recruitment and screening purposes. A waiver of documentation of consent and HIPAA authorization will be used in order to retain the preliminary eligibility screening responses (*see Screening Script*). Informed consent will be obtained prior to enrollment in the study.

Designated study staff and/or the PI will conduct the informed consent process. All study personnel will complete the necessary human subjects' protections training per VA policy. For study group 4 (remote study) informed consent will be conducted remotely. The consent document will be mailed/delivered to the participant. Designated study staff and/or the PI will conduct the informed consent process via phone. The participant will then mail (or researcher will pick up) the consent form and return back to the VA.

5.4 Inclusion/Exclusion Criteria

Our targeted range for the total number of study completions is up to 150.

Inclusion Criteria:

Participants with ankle OA:

1. radiographic evidence of tibiotalar OA
2. age 18 years or older
3. able to stand and walk for about an hour (with breaks) and at least 15m (about 50ft) at a time without difficulty
4. minimum pain 3+/ 10

Control participants without OA:

1. age 18 years or older
2. able to stand and walk for about an hour (with breaks) and at least 15m (about 50ft) at a time without difficulty

Exclusion Criteria: all participants

1. subtalar joint arthritis
2. prior ankle joint replacement or fusion on the foot of interest, or recent (<1 year) surgical, neurological, rheumatologic, or lower limb musculoskeletal problem (e.g., current foot ulcer, severe hip/knee OA, terminal illness, etc.) that impairs an individual's ability to do the walking tests
3. current user of AFO or rocker bottom shoe and has either been prescribed by doctor or is not willing to stop using the device for three months
4. plans to undergo surgical treatment for ankle OA within three months
5. inability to walk unassisted during short, repeated walking trials
6. rheumatoid arthritis
7. inadequate cognitive or language function to consent or to participate
8. no phone number or stable mailing address
9. currently incarcerated
10. currently pregnant
11. open wounds on the foot or ankle
12. below- knee surgery in the past 60 days

Additional Exclusion Criteria, Controls only:

1. Ankle pain or ankle OA in addition to the above exclusionary criteria

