SA 3: Compare the ankle OA clinical and biomechanical outcome measures for the control shoe, RB shoe, and AFO to a healthy control group wearing control shoes. This will determine the difference in clinical and biomechanical outcomes related to the presence of OA.

Methods: We will enroll 100 participants with ankle OA and 50 control participants without lower limb pain. Three study groups will participate in this project. Study group 1 is a single day study and have images taken using our biplane fluoroscopy system. Study group 2 is a three month take home, and Study group 3 is a three month take home and will have images taken using our biplane fluoroscopy system. At visit-1 all participants will do baseline measures (questionnaires and functional assessments, including **SSWS**) and have a CT scan. During the initial visit, group 1 will participate in a biplane assessment. Participants in Study group 2 & 3 will be assigned to a randomly selected order of footwear (RB shoe, control shoe or an AFO). Each footwear condition will be worn for a three-week trial period at-home/in-community (one-week acclimation, two-weeks continuous wear). Participants will complete brief weekly pain assessments and wear a step counter. At visit-2 participants will do a pain rating, repeat the questionnaires and SSWS test, and group 3 will have images taken using our biplane fluoroscopy system. Participants will continue wearing the step-counter during a one week washout period. For the next three weeks, participants will repeat the at-

home/in-community procedures (step counter, weekly pain rating) and come to the VA to repeat the visit-2 procedures. The same process will be repeated for the third footwear condition.

List of Abbreviations

Provide a list of all abbreviations used in the protocol and their associated meanings.

AE - adverse event

AFO - ankle-foot orthosis

CT - computed tomography

mSv - millisievert

OA - osteoarthritis

RB - rocker bottom

ROM - range of motion

ROP - report of other problem

SAE - serious adverse event

SSWS - self-selected walking speed

UW/HMC - University of Washington/Harborview Medical Center

Contents

Protocol Title: Do Rocker Bottom Shoes and Ankle-Foot Orthoses Reduce Pain and Improve Mobility for Ankle Osteoarthritis Patients?..... 6

1.0 Key Study Personnel..... 6

2.0 Introduction..... 6

3.0 Specific Aims and Hypotheses..... 7

4.0 Resources and Personnel..... 8

5.0 Study Procedures..... 8

 5.1 Study Design..... 8

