5.0 Study Procedures

5.1 Study Design

Participants in this research study will be men and women, age 18 and over, who can walk without difficulty for about an hour. People with and without ankle OA, will be enrolled. Targeted enrollment by ankle OA status is listed in the table below. Vulnerable populations will not be specifically targeted for enrollment. See inclusion/exclusion criteria below in section 5.4.

Study Groups	Total: 150
Controls, no ankle OA	50
People with Ankle OA	100

See section 5.5 below for data collection procedures and risk management.

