We will take video and photos of participants during portions of this study for documentation and use in research publications. All videos and photos will be anonymized (to avoid facial or voice identification) and tattoos and other distinguishing marks will be covered before images are captured or obscured during processing to protect the identity and privacy of our participants.

During study sessions, visitors and observers will not be allowed in the lab unless the participant agrees to their presence; the participant can change her/his mind at any time.

Study Footwear

Over the course of the study (one day or ~3 months) participants will be asked to wear up to three different footwear conditions: control shoes (a typical walking shoe, such as the New Balance 928), RB shoes (walking shoes with a front-to-back curved sole, such as the New Balance 928 with a rocker sole), and an orthotic device (such as an AFO, an ankle brace, such as the Toeoff[®] AFO) with control shoes. Participants will wear each footwear condition, in a randomized order. For all footwear conditions a fitbit zip may be clipped or taped to the shoe. This will record steps taken in the footwear. The fitbit will be synced during the VA visits and will only record number of steps. A separate account for each fitbit will be created and the account number will be recorded on the participant crosswalk. There will be no additional methods to link the data to the participant. Additional assessments on the initial day may include barefoot and own shoe as footwear conditions.

Screening /Eligibility Verification

Participants will have been preliminarily screened during recruitment, then during the first visit, after informed consent, we will make a final eligibility determination. This will include verifying that the information collected during recruitment is accurate and current.

If a participant cannot continue in the study, they will be compensated \$50 for the visit.

Demographic Data collection

Participants' age, sex, race/ethnicity and Veteran status will be recorded.

Anthropometrics

Participants' weight, waist circumference, and height will be measured.

Pain/health screening

Short survey which will include questions regarding trauma history in the lower limbs, joint replacements, OA, and pain throughout the body.

Functional Assessments

Self-selected Walking Speed (SSWS)

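### The abstract requires controls without lower limb pain, but Section 5.4 admits controls whose knee, hip or non-ankle foot pain does not impair walking, which clouds the Hypothesis 3.1 comparison

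*Combined protocol and SAP*

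**What the plan says.** The combined protocol and SAP describes the control group in four places.

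- Abstract, Methods: "We will enroll 100 participants with ankle OA and 50 control participants without lower limb pain".
- Section 5.1, enrolment table: "Controls, no ankle OA", with no condition on pain.
- Section 5.4, controls only: "Ankle pain or ankle OA in addition to the above exclusionary criteria".
- Section 5.6, Statistical Methods, Specific Aim 3: the group enters the model as an additional category, labelled healthy.

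Three other provisions bear on who can enter.

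- Exclusion 2 in Section 5.4, which applies to everyone, covers a "recent (<1 year) surgical, neurological, rheumatologic, or lower limb musculoskeletal problem" of the kind "that impairs an individual's ability to do the walking tests".
- Controls must be "able to stand and walk for about an hour (with breaks) and at least 15m (about 50ft) at a time without difficulty".
- The pain/health screening survey in Section 5.5 includes "questions regarding trauma history in the lower limbs, joint replacements, OA, and pain throughout the body". No eligibility rule is attached to it.

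**The concern.** Specific Aim 3 is meant to show what difference in clinical and biomechanical outcomes goes with having ankle OA. That reading depends on who the controls are. Staff screen against Section 5.4, so its looser rule decides who enters, while a reader of the abstract would take the comparator to be free of pain anywhere in the lower limb.

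Several Hypothesis 3.1 outcomes respond to pain at any site. The Brief Pain Rating asks for pain now, average pain and maximum pain without naming a joint. PROMIS pain interference and physical function, step count and walking speed are not tied to the ankle either. A control with a painful knee may score worse on all of these, and the Aim 3 model in Section 5.6 names no covariate for pain elsewhere. A report could then describe a pain-free comparator that the criteria did not guarantee, and its OA-control difference would contain an unknown contribution from other-site pain.

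**Working it through.** The plan states no figure on this point, so the check is mainly a comparison of texts.

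**Step 1: trace a test case through Section 5.4.** Take a prospective control with long-standing knee pain who can complete the walking tests.

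- Controls-only exclusion: not met, because the pain is not at the ankle and there is no ankle OA.
- Exclusion 2: not met. It needs a problem that is both recent and impairs the walking tests.
- Other exclusions for all participants (such as subtalar arthritis, rheumatoid arthritis, open foot or ankle wounds, and below-knee surgery in the past 60 days): not met.
- Walking inclusion criterion: met. This criterion is not a pain screen. Ankle OA participants must satisfy the same walking criterion and also have pain of at least 3 out of 10, so the protocol itself expects people with pain to pass it.

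Result: eligible under Sections 5.4 and 5.1, ineligible under the abstract. Hip pain or non-ankle foot pain that does not limit walking gives the same result. Such recruits are plausible, since Section 5.2 allows recruitment from the center's registry of people screened for or enrolled in its earlier studies.

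**Step 2: sort the Aim 3 outcomes.**

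- Not ankle-specific, so open to influence from other-site pain: step count, walking speed, PROMIS physical function, PROMIS pain interference, numeric pain rating.
- Foot and ankle instruments by name (FAOS, AOS-FAM): knee or hip pain need not shift these in the same proportion.
- Sagittal ROM (Hypothesis 3.2): no certain direction for knee or hip pain. Foot pain could alter midfoot ROM.

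**Step 3: illustrate size and direction.** Every input here except the enrolment targets of 100 and 50 is an assumption. Let D be the true effect of ankle OA on an outcome from the first set. Let f be the share of controls with other-site pain and g the share of OA participants with it. Suppose such pain adds s × D to a person's deficit in either group. Then

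observed contrast = D × [1 + (g − f) × s].

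- Pain in controls only (g = 0), f = 10% to 40%, s = 0.25 to 0.5: the factor runs from 1 − 0.10 × 0.25 = 0.975 to 1 − 0.40 × 0.5 = 0.80.
- Equal shares (g = f): the factor is 1.
- Pain in the OA group only (f = 0), same ranges for g and s: the factor runs from 1.025 to 1.20.

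For the first case, power for 100 versus 50 at two-sided 0.05 uses a standard error of √(1/100 + 1/50) = 0.173 SD. For a standardised difference of 0.5, power is 82% undiluted and 80% to 64% over the range. For 0.8 it is 99.6% undiluted and 99.5% to 96%. The plan gives no Aim 3 power to set against these values, because its Power Analysis covers only the shoe contrast in ROM.

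**The case against.** The strongest reply is that the comparator is a matter of choice. The exclusions that reach hip, knee and foot problems apply to both groups, so OA participants may also have non-limiting pain elsewhere. Allowing it in controls keeps the groups alike in that respect. Barring it from controls alone could credit other-site pain to ankle OA and overstate the deficit. This stands, and it shapes the remedy. It does not remove the contradiction, because it is not the comparator that the abstract declares.

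A reader might infer three stronger things that the documents do not support.

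- That Section 5.4 bars nothing in controls beyond ankle pain and ankle OA. The same line keeps all the general exclusions, so severe or walking-limiting hip, knee and foot problems can already be excluded.
- That every Aim 3 difference is diluted by some set percentage. The direction is uncertain for ROM, the foot and ankle scores need not move in proportion, and any percentage is a product of assumed numbers.
- That the OA deficit is necessarily underestimated. With other-site pain in both groups, Step 3 shows that the error can go either way or cancel.

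Two further cautions are fair. The Screening Script attachment is not available here and may ask controls about lower limb pain. The plan is also unclear about which Hypothesis 3.1 data controls supply. The take-home groups are described as ankle OA participants, and the activities listed for study group 1 omit the questionnaires and home step monitoring. Yet the abstract has everyone complete questionnaires at the first visit, and the biplane section has group 1 return a StepWatch. Neither caution reconciles the written definitions.

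**Conclusion.** The point holds as an inconsistency in the definition of the control group, with a possible effect on the Hypothesis 3.1 outcomes that are not ankle-specific. Taken alone, other-site pain in controls would move those outcomes towards OA values. The net bias depends on how common such pain is in each group, and the documents do not say. Its size cannot be derived from them; the factors of 0.80 to 1.20 rest wholly on the assumed shares and the additive model. No claim is made about the direction for Hypothesis 3.2. This is a worthwhile, inexpensive correction and not a flaw that invalidates Aim 3. It does not affect the shoe comparisons within OA participants in Aims 1 and 2, which use no controls.

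**What to change.** 1. Reconcile the abstract, Section 5.1 and Section 5.4. Either carry the abstract's condition of no lower limb pain into the controls-only criteria, or correct the abstract and the healthy-control label in Section 5.6 to match the group actually admitted. Both are acceptable; the choice should be stated.
2. Whichever is chosen, prespecify an Aim 3 sensitivity analysis that excludes controls who report lower limb pain on the pain/health survey. This also covers controls already enrolled. Confirm that every participant completes the survey and that it records the site of pain.
3. Because OA participants may have pain elsewhere too, repeat that analysis with OA participants reporting non-ankle lower limb pain also excluded, or with other-site pain as a covariate, so that such pain is not attributed to ankle OA.

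Cost: slightly slower control recruitment if eligibility is tightened, a small loss of sample in the sensitivity analyses, and a little more analysis. No new procedure is needed if the survey already records site.

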5.5 Study Visits, Data Collection, and Risk Management

Participants can be enrolled in one of three study groups for this project. The specific procedures for each item are outlined below.

Visits at the VA Puget Sound may last up to 4 hours each. Participant schedules and the accessibility of facility resources may extend the study timeframe beyond these estimates. Study visits will be scheduled by contacting the participants on phone, or during in-person contacts. We may contact participants with appointment and/or at home activity reminders via email or phone.

Study group 1: One day visit

Participation will be at the VA Puget Sound and last up to 4 hours wearing the participants own or study provided footwear during the activities. Activities may include a Screening, Functional assessments, CT scan with pregnancy test, Qualitative questions, Brief Pain Rating, and a Biplane assessment with one or more interventions including barefoot, their own footwear, a modified shoe (such as a rocker bottom shoe), an orthotic device (such as an AFO), or a control shoe provided by the researchers.

Study group 2: Take home portion only (~3 months)

Participants with ankle OA will conduct a initial visit that will include a Screening, Functional assessments, CT scan with pregnancy test, Questionnaires, Qualitative questions, and Brief Pain Rating followed by a 3 month intervention at home intervention, that will include three additional visits to the VA. Timeline and assessments during those visits is described below.

Study group 3: Take home portion with Biplane (~3 months)

This study group is similar to Study group 2, however it does include three biplane assessments over the three additional visits.

Study group 4: Remote take home only (~ 3 months)

This study group is similar to Study group 2, however all procedures will be done remotely. Participants with ankle OA will conduct a initial assessment that will include a Screening, Functional assessments, Questionnaires, Qualitative questions, and Brief Pain Rating followed by a 3 month at home intervention, that will include three additional assessments. Timeline and assessments during those assessments is described below. In addition, we will ask you to wear a StepWatch Activity Monitor (a step counter) and to do brief weekly pain ratings, and daily pain rating and pain medication use over the course of the entire study.

Photos and video

We will take video and photos of participants during portions of this study for documentation and use in research publications. All videos and photos will be anonymized (to avoid facial or voice identification) and tattoos and other distinguishing marks will be covered before images are captured or obscured during processing to protect the identity and privacy of our participants.

During study sessions, visitors and observers will not be allowed in the lab unless the participant agrees to their presence; the participant can change her/his mind at any time.

Study Footwear

Over the course of the study (one day or ~3 months) participants will be asked to wear up to three different footwear conditions: control shoes (a typical walking shoe, such as the New Balance 928), RB shoes (walking shoes with a front-to-back curved sole, such as the New Balance 928 with a rocker sole), and an orthotic device (such as an AFO, an ankle brace, such as the Toeoff[®] AFO) with control shoes. Participants will wear each footwear condition, in a randomized order. For all footwear conditions a fitbit zip may be clipped or taped to the shoe. This will record steps taken in the footwear. The fitbit will be synced during the VA visits and will only record number of steps. A separate account for each fitbit will be created and the account number will be recorded on the participant crosswalk. There will be no additional methods to link the data to the participant. Additional assessments on the initial day may include barefoot and own shoe as footwear conditions.

Screening /Eligibility Verification

Participants will have been preliminarily screened during recruitment, then during the first visit, after informed consent, we will make a final eligibility determination. This will include verifying that the information collected during recruitment is accurate and current.

If a participant cannot continue in the study, they will be compensated \$50 for the visit.

Demographic Data collection

Participants' age, sex, race/ethnicity and Veteran status will be recorded.

Anthropometrics

Participants' weight, waist circumference, and height will be measured.

Pain/health screening

Short survey which will include questions regarding trauma history in the lower limbs, joint replacements, OA, and pain throughout the body.

Functional Assessments

Self-selected Walking Speed (SSWS)

Participants wear either their own footwear or researcher provided footwear. Participants will be asked to walk 20 meters in a straight line, at their own pace, in the hallway while a researcher times how long each walk takes. This will be used to determine the participants' self-selected walking speed (SSWS). This assessment will be conducted up to three times and averaged.

Timed Up and Go (TUG)

Participants wear either their own footwear or researcher provided footwear. Participants will start seated in a chair with arm rests, stand up, walk to a line 3 meters away, turn around, walk back to the chair, then sit down. Time to complete this will be recorded. This assessment will be conducted up to three times and averaged.

10 m fast walking test (10 m walk)

Participants wear either their own footwear or researcher provided footwear. Participants will be instructed to walk as fast as they are comfortable for 10 meters. Participants will start walking before the 10 meter line and continue past the finish line. Time to complete the 10 meter walk will be recorded. This assessment will be conducted up to three times and averaged.

Qualitative Assessment

Participants will be asked several questions and responses will be recorded.

1. Do you like the device? Why/ why not?
2. Would you continue to wear the device if you were not part of the study? Why/why not?
3. Do you have a preference to one of the treatments? Which one? Why?

Questionnaires

Participants will be asked to complete a series of questionnaires about their pain and physical function. This will include the Patient Reported Outcomes Measurement Information System (PROMIS) pain interference v1.1, PROMIS physical function v1.2, and the Foot Ankle Ability Measure (FAAM).

The PROMIS measures will be completed on a mobile tablet and the data is saved locally by the application. The participant will enter their responses or it may be conducted as an interview with staff entering responses. The PROMIS measures are computer adaptive tests – the responses to the items determine which question path the user is taken through. Only a study assigned ID code (e.g., RBAFO_OA_001) will be associated with the PROMIS data. The other measures will be administered on paper or as an interview and will also be labeled with the study ID code. See section 10 for additional Privacy and Information Security details.

Daily Pain Rating and Pain Medication Use

We may ask you to rate (on a scale of 1-10) what your pain level is now, what your average pain level was in the past 24 hours, and what your maximum pain level was in the past 24 hours. We may also ask you what if any pain medication you took.

Brief Pain Rating (BPR)

A brief three item pain rating (1) what is your pain level now (0-10)?, 2) what has been your average pain level this week (0-10)?, and 3) what was your maximum pain level this week (0-10)?).

StepWatch Activity Monitor

A StepWatch Activity Monitor and instruction sheet will be provided to the participants. The StepWatch Activity Monitor is a step-counter placed around the ankle and is to be worn at home and in the community.

Pregnancy test

At each visit that involves exposure to radiation female participants of child-bearing potential (under age 50) will undergo a pregnancy test (urine test) so we can verify that they are not pregnant. Designated study staff will escort female participants to the bathroom and provide them with a specimen cup, pregnancy test strip, and a disposable container on which to place the used test strip. Staff will go over the test instructions, and verify the test result. Staff will not handle urine specimens, we will tell participants how to handle and dispose of the materials. Pregnancy tests may also be conducted by the lab at the VA Puget Sound. If the test indicates that the participant is pregnant she will be not be able to participate in the study and we will advise her to see her regular clinical care provider.

CT Scan

CT scans will be done at the VA Puget Sound, however, if needed, CT scans may be collected by a third-party vendor on a fee for service basis as explained below. We hope to do the CT scan during the first visit, however the scan may be taken during any of the study visits depending on scheduling needs.

If participants have a VA or UW medical record(s) we will access them to collect information related to participants' foot/ankle diagnosis, related clinical treatment, and check to see if they have already had a CT scan that can be used for this study. If participants report that they have had a CT scan(s) at a different medical facility, we may request copies of them. If possible, we will use the previously collected images for our data set and analyses so that participants do not have to be exposed to additional radiation. We will search for CT scans that took place within the last 5 years. If participants' medical records are not at the VA they will be asked to sign a release form so that

we can obtain copies of these records. The CT scans and any other requested clinical notes from outside the VA will be delivered via the following methods:

- The images and other clinical treatment information may be burned to CD(s) or DVD by HMC or other facility and mailed to us via traceable shipping.
- A designated study staff member will pick up the CD(s) or DVD from HMC/UW or other facility and transport it to the VA.
- Information about lower extremity diagnoses and clinical treatment may be provided to designated study staff over the phone – the information will be labeled with the participants' study code and added to study records

(B) If scheduling a CT scan at the VA Puget Sound proves to be difficult, we may schedule the CT scan at a third-party vendor (i.e., a fee for service CT scanner). The vendor will use the Study Staff's name and a study ID code for scheduling purposes. We will provide participants with the address of the vendor. A study ID code (e.g., RBAFO_OA_01) will be entered in the name field of the CT scan file along with age in years (if 89 or younger). The vendor will not store subjects' PHI in their files and they will not have access to or create a study ID crosswalk. The vendor will make a copy of the CT scan with the study ID code and age. Study staff will pick up the CD and transport the scan to the VA and/or the vendor mail it to us via traceable shipping.

Additionally, a low dose CT scan of participants may be taken using our Center's LineUP system (<http://www.curvebeam.com/products/lineup/>) and/or using clinical resources at the VA Puget Sound. The scan will start at the mid-tibia (lower leg) and extend down to include the subject's feet. The CT scan will be used to generate a computational model of the participant's bony anatomy – a necessary step for generating results with the fluoroscopy system.

Participants will be instructed to perform up to 15 scans in various positions including: barefoot partial weight-bearing neutral position, barefoot partial weight-bearing maximum ankle dorsiflexion, barefoot partial weight-bearing maximum plantarflexion, full weight-bearing barefoot in neutral position, and partial weight-bearing with 3 different footwear in a secured manner to sustain the posture while scanning. Repeated procedure may be necessary as the scan requires the participant to maintain the static position for less than one minute.

Biplane Fluoroscopy Laboratory

These procedures are utilized in study groups 1 and 3. Participants will be escorted to the Biplane Fluoroscopy Lab per our SOPs. While wearing shorts (their own or ones we provide) and the assigned footwear (barefoot, own shoe, rocker bottom (RB) shoes, control shoes, or an ankle-foot orthosis (AFO) with the control shoes) the participants will step onto an elevated walkway, which is flat, about 3 feet wide, level, and has handrails on both sides. Participants will walk freely up and down the walkway to get comfortable with the test environment.

While standing still on the platform, a force plate will capture ground reaction forces and two fluoroscopes will capture simultaneous X-ray images of the participant's foot of interest to record the standing position of the bones. These dual fluoroscopes allow for tracking of the bone motion in three dimensions while the participant is walking. Next, participants will walk along the platform

while simultaneous X-ray images of the foot of interest are taken; each X-ray exposure is expected to last about 0.5 seconds, and will image from about 3 inches above the ankle to below the bottom of the shoe or foot. Participants will do up to 26 walking trials with each footwear condition during which images of their foot are taken. For some participants, we may take images of both feet during the standing and walking X-ray procedures. Rest breaks will be provided as needed.

Over the course of the study, participants with ankle OA will repeat the biplane fluoroscopy session 3 times (once for each footwear condition). Participants in study group 1 will complete the biplane in one session while barefoot, or wearing their own shoes, the control shoes, RB shoes, and/or the AFO. Each participant will receive no more than 80 total biplane imaging trials as part of the study.

Participants enrolled in study group 3 will continue wearing the StepWatch. Those in study group 1 have completed their participation and will return the study footwear and StepWatch.

Take home study

Length of participation

For participants with ankle OA, study procedures will occur over ~3 months (11 weeks). Four study visits will be done at the VA Puget Sound where three at-home/in-community study footwear (control shoes, RB shoes, an AFO) condition periods will be conducted.

Visits at the VA Puget Sound may last up to 4 hours each. Participant schedules and the accessibility of facility resources may extend the study timeframe beyond these estimates. Study visits will be scheduled by contacting the participants on phone, or during in-person contacts. We may contact participants with appointment and/or at home activity reminders via email or phone.

Assessment 1

During this initial assessment participants will complete the, Screening, Functional assessments, LineUP with pregnancy test (not Study group 4), Questionnaires, and Brief Pain Rating. Participants will be given a StepWatch and the first footwear condition. At the first assessment, participants who elect to use Ilumivu will be assigned a randomized username for the ilumivu mobile application. The link between this unique ID and the Veteran's identity will not be stored in the mobile application, but rather, stored locally at the Seattle VA. Further information about data security can be found in the Data Security section of this application. Ilumivu, is an app downloaded onto your phone. This app and its developers do not have any information that can be linked back to the participant. Only the researchers will know the Ilumivu participant ID. The Ilumivu participant ID will be recorded on the participant crosswalk in the research folder on the R drive. There will be no additional methods to link the data to the participant.

In Home/Community - Footwear Condition 1: Acclimation and Continuous Wear Period (3 weeks)

On day-1 of the first at home period, participants will wear the study footwear for one hour, then for two hours on day-2, three hours on day-3, then continue adding one hour of wear per day until the seventh day is reached. For the next two weeks, participants will wear the study footwear throughout the day during their normal daily activities. Participants will wear the StepWatch throughout this 3-week period. Each day participants will receive two messages either via email or with Ilumivu from the study staff, one in the morning, reminding the participant to wear the selected

footwear for the suggested number of hours, and one in the evening, reminding the participant to record the number of hours he/she has worn the selected footwear.

Once per week we will call/email/ message through Ilumivi (which ever the participant prefers) participants to check in and complete the Brief Pain Rating and Qualitative assessment.

Participants will be instructed to contact us if they have questions or if the study footwear is painful/uncomfortable. We will address any issues on an as needed basis, which may require additional visits to the VA.

If a proper and comfortable fit cannot be achieved with a footwear condition, then participants may wear their own shoes for a one-week washout period (while continuing other study procedures) and we will move them to the next footwear condition if they wish to continue their participation. If we determine that it is not in the participant's interest to continue in the study he/she will be withdrawn.

Assessment 2

After the 2-week continuous wear period, participants will come to the VA Puget Sound with the StepWatch and study footwear. The StepWatch data will be downloaded and participants will complete the Brief Pain Rating, Qualitative assessment, Questionnaires, and Functional assessments. For those enrolled in Study group 3, the Biplane assessment will be conducted during this visit using the current footwear condition.

Participants will be given instructions for the second footwear condition.

In Home/Community Footwear Condition 1 Washout Period (1 week)

For the next week, participants will be asked to wear their own self-selected footwear, continue wearing the StepWatch and complete the weekly pain rating over the phone.

In Home/Community – Footwear Condition 2: Acclimation & Continuous Wear Period (3 weeks)

Participants be asked to follow the same 1-week acclimation procedure, followed by 2-weeks of continuous wear that they did with Footwear Condition 1. Participants will be asked continue wearing the StepWatch and complete the weekly pain ratings.

Assessment 3

The procedures described in Assessment 2 will be repeated.

In Home/Community Footwear Condition 2 Washout Period (1 week)

[figure not shown]
Participants will repeat the procedures described under In Home/Community Footwear Condition 1 Washout Period.

[figure not shown]
In Home/Community Footwear Condition 3: Acclimation & Continuous Wear Period (3 weeks)

Participants be asked to follow the same 1-week acclimation procedures, followed by 2 weeks of continuous wear that they did with Footwear Conditions 1 and 2. Participants will also continue wearing the StepWatch and completing weekly pain ratings.

Assessment 4

The procedures described under Assessment 2 will be repeated. Participants will return the study footwear and the StepWatch.

Registry (optional)

Participants will be asked if they are interested in joining our Center’s Subject Registry (MIRB# 00433). This registry is used to recruit for studies being conducted by our Center. If participants choose to join the registry they will sign a separate consent form. Data about their foot type that is collected under this study will be added to the Subject Registry; this will help us determine which studies may be a good fit for participants in the future.

Repository (optional)

Participants will be asked if they are interested in allowing their study data to be added to our de-identified data repository so that it may be used for additional research in the future. Participants who are interested will be asked to sign a separate consent form for the repository (MIRB# 00493). Once the consent form is signed, a copy of the data will be added to the repository on an ongoing basis throughout the course of the study.

Additional use of de-identified data

Throughout the course of the study we will place a copy of all de-identified data in publicly accessible online data repositories. Once posted, the de-identified data will publicly accessible to search, retrieve, and analyze for any purpose. Participants will be made aware of this use of de-identified data during the consent process and it will be described in the consent form. If participants do not wish to have a copy of their de-identified data placed in online repositories they can choose not to participate in the study.

Payment to Participants

Participants will be paid once at the end of the study. Participants in study group 1 will receive \$30/hour after they complete all of the study procedures. Participants in study groups 2 and 3 will receive \$400 and \$500 respectively, participants in study group 4 will receive \$300, after they complete all of the study procedures. If participants are withdrawn early they will be paid based on a daily prorated amount for the length of time they were expected to be in the study.

Checks will be mailed by the fiscal department about 6-8 weeks after each study visit or participants can pick up their check at the VA Puget Sound in approximately the same time frame. Participants that are screened out after consent will be compensated \$50 for their good faith effort.

Risks and Risk Management

Procedures Involving Radiation Exposure

